2.7.1 Telephone Contacts (Between Visit 4 and Visit 5)

The subject should be contacted by phone twice between clinic appointments at one month intervals to ensure she is following the instructions for use, is not experiencing any technical or

medical problems while wearing the Eclipse Insert, and to remind her to complete the Treatment Diary at the required time.

2.7.2 Visit 5 – 3 Months (\pm 2 weeks) after Visit 4

Subjects are evaluated for the frequency of their FI episodes according to their two week Treatment Diary, and are evaluated for continued fit and safety of the Eclipse Insert.

The following tasks are completed at this visit:

- Two week Treatment Diary reviewed
- St. Mark's (Vaizey) Incontinence Severity Score calculated
- FIQOL questionnaire administered
- PGI-I questionnaire administered
- Patient Goal questionnaire administered
- Cost Utilization survey administered
- Device Satisfaction questionnaire administered
- Pelvic exam (speculum and digital rectal exam)
- AEs and Concomitant Medications reviewed
- Two week Treatment Diary dispensed (for use prior to the 6 month visit)

The subject is re-counseled on the requirements of the Treatment Period of the protocol, on the proper use and care of the Eclipse System (**Appendix 9**) and proper completion of the Treatment Diary.

The subject is instructed to complete the Treatment Diary while wearing the Eclipse Insert for a consecutive 14-day (2 week) period just prior to the next scheduled visit.

2.7.3 Telephone Contacts (Between Visit 5 and Visit 6)

The subject should be contacted by phone twice between clinic appointments at one month intervals to ensure she is following the instructions for use, is not experiencing any technical or medical problems while wearing the Eclipse Insert, and to remind her to complete the Treatment Diary at the required time.

2.7.4 Visit 6 – 6 Months (\pm 2 weeks) after Visit 4

Subjects are evaluated for the frequency of their FI episodes according to their two week Treatment Diary, and are evaluated for continued fit and safety of the Eclipse Insert.

The following tasks are completed at this visit:

- Two week Treatment Diary reviewed
- St. Mark's (Vaizey) Incontinence Severity Score calculated
- FIQOL questionnaire administered
- PGI-I questionnaire administered
- Patient Goal questionnaire administered
- Device Satisfaction questionnaire administered
- Pelvic exam (speculum and digital rectal exam)
- AEs and Concomitant Medications reviewed

The subject is re-counseled on the requirements of the Treatment Period of the protocol, and on proper use and care of the Eclipse System (**Appendix 9**). A Treatment Diary is not dispensed at Visit 6 and is not required to be completed by the subject prior to Visit 7.

2.7.5 Telephone Contacts (Between Visit 6 and Visit 7)

The subject should be contacted by phone twice between clinic appointments at one-month intervals to ensure she is following the instructions for use and is not experiencing any technical or medical problems while wearing the Eclipse Insert.

2.7.6 Visit 7 – 9 Months (\pm 2 weeks) after Visit 4

Subjects are evaluated for continued fit and safety of the Eclipse Insert.

The following tasks are completed at this visit:

- St. Mark's (Vaizey) Incontinence Severity Score calculated
 - FIQOL questionnaire administered
 - PGI-I questionnaire administered
 - Patient Goal questionnaire administered
 - Device Satisfaction questionnaire administered
 - Pelvic exam (speculum and digital rectal exam)
 - AEs and Concomitant Medications reviewed
- Two week Treatment Diary dispensed (for use prior to the 12 month visit)

The subject is re-counseled on the requirements of the Treatment Period of the protocol, on proper use and care of the Eclipse System (**Appendix 9**) and proper completion of the Treatment Diary.

The subject is instructed to complete the Treatment Diary while wearing the Eclipse Insert for a consecutive 14-day (2 week) period just prior to the next scheduled visit.

2.7.7 Telephone Contacts (Between Visit 7 and Visit 8)

The subject should be contacted by phone twice between clinic appointments at one month intervals to ensure she is following the instructions for use, is not experiencing any technical or medical problems while wearing the Eclipse Insert, and to remind her to complete the Treatment Diary at the required time.

2.7.8 Visit 8 – 12 Months (\pm 2 weeks) after Visit 4

Subjects are evaluated for the frequency of their FI episodes according to their two week Treatment Diary, and for safety of the Eclipse Insert.

The following tasks are completed at this visit:

- Two week Treatment Diary reviewed
- St. Mark's (Vaizey) Incontinence Severity Score calculated
- FIQOL questionnaire administered
- PGI-I questionnaire administered
- Patient Goal questionnaire administered
- Cost Utilization survey administered
- Device Satisfaction questionnaire administered
- Pelvic exam (speculum and digital rectal exam)
- AEs and Concomitant Medications reviewed

2.7.9 Unscheduled Visits

A subject may return to clinic at any point during the Screening Period or Treatment Period, if needed. During an Unscheduled Visit, the investigator may perform a standard medical interview and physical examination, including a pelvic examination or Insert re-sizing, if appropriate. All assessments, and any abnormal findings, including AEs and/or product malfunctions, will be documented in the appropriate case report forms.

2.8 Re-sizing during Treatment Period

If at any time during or after Visit 5 (the 3-month time point visit), an Insert no longer fits appropriately as assessed by a clinician during a pelvic exam, re-sizing of the Insert may be performed. The Insert may be re-sized at the treatment visit or at an Unscheduled Visit in between Treatment Visits per the following steps:

1. If changing to a different Sized Insert, use one or more of the Sizers to determine the next appropriate sized Trial Insert, and send the subject home with the Trial Insert. Complete a Fitting CRF, and order the corresponding Eclipse Insert from Pelvalon immediately so it arrives in time for the follow-up Fit Confirmation Visit. Complete either the Treatment Pelvic Exam CRF or an Unscheduled Visit CRF, as appropriate.
2. Schedule a follow up visit within 7 days (-5/+7 days) to confirm the Trial Insert fit is comfortable and stable by pelvic exam. The follow up visit should be scheduled as close to 7 days post-fitting as possible to allow the subject enough time to accommodate to the device. However, the subject should be seen earlier in the window (as soon as possible) if they are experiencing signs of an improper fit (discomfort or lack of effectiveness), an adverse event or any of the following:
 - Foul odor or excessive vaginal discharge
 - Any difficulty urinating or defecating
 - Significant bleeding not associated with menstruation
 - Unusual pelvic pain or discomfort
3. If successfully re-sized, dispose of the Trial Insert and dispense the same sized Eclipse Insert and instruct the subject to begin her next Treatment Diary as scheduled. The start of the Treatment Diary should be delayed, if necessary, so that it begins seven days or more after the newly sized Eclipse Insert is dispensed.
4. Steps 1-3 may be repeated as needed.

2.9 Study Exit

A Study Exit CRF will be completed for each subject who is consented in the trial. Participation in the study is considered complete if the subject completes all end-of-study assessments and questionnaires at the final 12 month time point.

A subject's participation may be discontinued early for any of the following reasons:

- Failure to meet screening eligibility criteria at any time after Visit 2
- Withdrawal of consent
- Adverse event preventing further study participation
- Investigator decision / determination that it is in the subject's best interest
- Termination of the study for any reason
- Lost to follow-up: requires documentation of at least 3 attempts to contact the subject by phone and/or email, and a certified letter (with request to return the investigational device)
- Subjects who become pregnant will be discontinued from the trial

For all subjects who were fit with the Eclipse System at Visit 2 and exit the study prior to or at Visit 4 (Treatment Eligibility Visit), AEs and ConMeds will be reviewed and a pelvic exam and the Device Satisfaction questionnaire will be administered, as per **Table 3**.

For subjects who exit the study after Visit 4 (Treatment Eligibility Visit) but before Visit 8 (12 Months) AEs and ConMeds will be reviewed, and a pelvic exam and all required questionnaires per **Table 3** will be administered.

To compensate for time spent during study visits, subjects may receive compensation as detailed in the final IRB-approved consent form and as agreed upon by the Sponsor and the Site per the Clinical Trial Agreement.

2.10 Questionnaires and Surveys

2.10.1 FI Episode Diary

Subjects will be provided a Diary (**Appendix 2**) to record each bowel movement, including the type of episode (normal bowel movement, staining, minor soiling or major soiling), whether the bowel movement was “urgent” (yes or no) and the stool description according to the Bristol Stool Score (ranging from 1 “separate hard lumps” to 7 “liquid consistency with no solid pieces”). The Baseline Diary is dispensed at Visit 1 (Baseline Visit), the Test Diary is dispensed at Visit 3 (Fit Confirmation Visit), and the Treatment Diary is dispensed at Visit 4 (Final Eligibility Visit), and at the 3 month and 9 month scheduled visits during the Treatment Period. The Test Diary and the Treatment Diary also ask if the subject is wearing the Insert at the time of each recorded episode.

Only minor or major soiling are counted towards the number of FI episodes in any two-week diary period, used in the study endpoint analyses (see **Section 3.2**).

2.10.2 St. Mark’s (Vaizey) Incontinence Severity Score

The St. Mark’s (Vaizey) Incontinence Severity Score is a measure of severity of FI symptoms, which has been shown to correlate with improvement in frequency of FI episodes and subjects’ perceptions of relief.^{23,24,25} This score reflects the severity of FI and ranges from 0 (complete continence) to 24 (complete incontinence). The survey will be administered verbally to subjects by site personnel at Visit 1 (Baseline Visit), and at 3, 6, 9 and 12 months during the Treatment Period.

2.10.3 Fecal Incontinence Quality of Life Questionnaire

The Fecal Incontinence Quality of Life (FIQOL) scale (**Appendix 3**) is a 41-item, validated questionnaire completed by the subject.²⁶ FIQOL has 4 subscales: lifestyle, coping/behavior, depression/self-perception and embarrassment. The FIQOL questionnaire will be completed by subjects at Visit 1 (Baseline Visit) and at 3, 6, 9 and 12 months during the Treatment Period.

2.10.4 PGI-I Questionnaire

The Patient Global Impression of Improvement (PGI-I) (**Appendix 4**) is a validated global index that may be used to rate the response of a condition to a therapy on a scale from 1 (Very much better) to 7 (Very much worse). It is a simple, direct, easy to use scale that is intuitively

²³ Vaisey, CJ, et al Gut 1999;44:77-80 doi:10.1136/gut.44.1.77

²⁴ Deutekom M, Terra MP, Dobben AC, Dijkgraaf MG, Felt-Bersma RJ, Stoker J, Bossuyt PM: Selecting an outcome measure for evaluating treatment in fecal incontinence. *Dis Colon Rectum* 2005, 48:2294-2301.

²⁵ Maeda Y. Does the St. Mark's incontinence score reflect patients' perceptions? A review of 390 patients. *Dis Colon Rectum*. 2008 Apr;51(4):436-42

²⁶ Rockwood et al. Fecal Incontinence Quality of Life Scale. *Dis Colon Rectum* 2000;43:9-16.

understandable to subjects and to clinicians. To date it has been most often used to assess the subjects' response to various treatments for urinary incontinence.²⁷ In this study we used the PGI-I questionnaire, replacing urinary incontinence with fecal incontinence, to assess the subject's response to treatment with the Eclipse System for fecal incontinence. The PGI-I questionnaire will be completed by subjects at 3, 6, 9 and 12 months during the Treatment Period.

2.10.5 Patient Goal Questionnaire

At the Visit 2 subjects will be asked to specify a single patient-centered goal describing what a successful improvement in FI symptoms would mean for them. For example, they may identify "confidence in attending social events" or "ability to exercise without incontinence." At the 3, 6, 9 and 12 month visits subjects will rank how well they were able to meet their goal while wearing the Eclipse Insert using a 7-point scale (**Appendix 5**) ranging from "I have met and exceeded my goal" (best case) to "I have moved further away from my goal" (worst case). The patient goal categories are based on results from a survey of women undergoing pelvic floor dysfunction surgery.²⁸

2.10.6 Device Satisfaction Questionnaire

Subjects who are fit at least once with the Trial or Eclipse Insert will be asked to complete a Device Satisfaction Questionnaire (**Appendix 6**). The questionnaire contains questions related to perceptions of device comfort, satisfaction with usage and features, and impact on daily activities.

Subjects who Screen Fail but have been fit at least once with the Insert will be asked to complete this questionnaire just prior to their study exit. Subjects who successfully enter the Treatment Period will be asked to complete this questionnaire at 3, 6, 9 and 12 months during the Treatment Period (or at study exit if they end their participation in the trial early).

2.10.7 Cost Utilization Survey

Subjects will be asked to complete a Cost Utilization survey (**Appendix 10**) in order to capture the direct medical and non-medical (out of pocket) and indirect non-medical costs related to treating FI in the three months prior to Visit 1 (Baseline Visit) and again at the 3 and 12 month time points. The data will be used to perform a cost analysis of the Eclipse System compared to alternative therapies.

3 Statistics

3.1 Study Design

This is a 1-year, multicenter, within-subject control, open-label, single-arm study to evaluate the durability of the safety and effectiveness of the Eclipse™ System after 3 and 12 months of use. All subjects will act as their own control. Subjects will be fitted, and refitted if necessary, with the Trial Insert during the Screening Period. Subjects who successfully complete the Screening Period will be considered as treatment-eligible and will be fitted with the Eclipse Insert and begin the 12 month Treatment Period. Subjects who do not successfully complete the Screening Period will be classified as screen fails and will not continue into the Treatment Period.

²⁷ Yalcin I, Bump R. Validation of two global impression questionnaires for incontinence. *Am J Obstet Gynecol* 2003;189:98-101.

²⁸ Kathie L. Hullfish, Viktor E. Bovbjerg, Jennifer Gibson, William D. Steers Patient-centered goals for pelvic floor dysfunction surgery: What is success, and is it achieved? *American Journal of Obstetrics and Gynecology, Volume 187, Issue 1, July 2002, Pages 88-92*

3.2 Derivations and Definitions

The **baseline period** is the period prior to the Initial Fitting Visit. Results from this period, using either the Baseline Diary or assessments conducted at Visit 1, will be the **baseline results**.

Change from baseline is calculated as (visit result) – (baseline result).

Percent change from baseline is calculated as $100 * (\text{change from baseline}) / (\text{baseline result})$.

An **FI episode** is defined as major soiling or minor soiling, but does not include staining alone, as recorded on Baseline Diary, Test Diary or Treatment Diaries, each defined as follows:

- **Staining:** Stain of stool on undergarment, pad, clothing, or skin (does not count as an FI episode).
- **Minor soiling:** Stool leakage that is more than staining, but did not require an immediate change of undergarment, pad, or clothing (e.g. a pebble sized piece of stool or teaspoon of liquid stool).
- **Major soiling:** An accident large enough to require an immediate change of undergarment, pad, or clothing (e.g. most of a bowel movement).

A bowel movement is defined as **urgent** if the subject checks: "I had to rush to the restroom immediately." Note: "Urgent" can be marked regardless of whether you made it to the toilet in time (for a normal bowel movement) or not (resulting in leakage)."

The following will be calculated for each diary period using the information entered in the FI Episode Diaries for each subject (Baseline Diary, Test Diary, and Treatment Diaries):

Average number of FI episodes per week: $7 * (\# \text{ episodes}) / (\# \text{ days of diary entry})$

Average number of FI days per week: $7 * (\# \text{ of days with } \geq 1 \text{ FI episode}) / (\# \text{ days of diary entry})$

Screen Failure: A subject who does not successfully complete the Screening Period. This could be due to failing any of the general inclusion/exclusion criteria such as age or FI frequency by baseline diary assessment, unsuccessful fitting (as determined before or at Visit 4), failure to record a minimum of 12 days of diary data after successful fitting (i.e. Test Diary), or failure to demonstrate a 50% or greater reduction in the average number of FI episodes in the Test Diary as compared to the Baseline Diary.

Treatment-eligible Subject (Enrolled): A subject who successfully completes the Screening Period and enters the Treatment period is considered enrolled. This is defined as a subject having a confirmed successful fitting (as determined at Visit 3), having recorded a minimum of 12 out of 14 consecutive days of diary data after a successful fitting (i.e. on their Test Diary), and having demonstrated at least a 50% reduction in the average number of FI episodes in the Test Diary at Visit 4 as compared to the Baseline Diary.

Treatment Responder: An enrolled subject who demonstrates at least a 50% reduction in the average number of FI episodes per week on her Treatment Diary compared to her Baseline Diary is a responder for that time period. An enrolled subject must also have at least 10 out of 14 consecutive days of recorded diary data on her Treatment Diary to be defined as a responder for that time period.

Treatment Non-Responder: An enrolled subject who does not demonstrate at least a 50% reduction in the average number of FI episodes per week on her Treatment Diary compared to her Baseline Diary, is a non-responder for that time period. An enrolled subject with less than 10 out of 14

consecutive days of recorded diary data on her Treatment Diary will also be classified as a non-responder for that time period.

3.3 Analysis Populations

The Safety Population will include all subjects exposed to any part of the Eclipse System during or after Visit 2 (Initial Fitting Visit). This will include all subjects who were unsuccessfully fitted, and screen failures. This will be the primary analysis population for all safety analyses.

The Intent-to-Treat (ITT) Population will include all subjects who are successfully fit with the Eclipse Insert, successfully complete Visit 4, and enter the Treatment Period.

The Per-Protocol (PP) Population will include all subjects in the ITT population who complete Visit 5 (Month 3 Visit), complete at least 10 out of 14 consecutive days of diary data at each time point in the study Treatment Period, and have no major protocol deviations.

3.4 Hypotheses

The null hypothesis is that the proportion of treatment responders at 3 months is no more than 40%, and the alternative hypothesis is that the proportion of treatment responders at 3 months is more than 40%:

$$H_0: \pi \leq 0.40$$

$$H_A: \pi > 0.40$$

3.5 Endpoints

The primary effectiveness endpoint is the proportion of treatment responders at the 3 month time point in the ITT population.

Secondary effectiveness endpoints are:

- The proportion of responders at the 3, 6 and 12 month time points in the PP population.
- The change from baseline in mean scores on subject-reported outcomes related to symptoms and quality of life as reported by St. Mark's (Vaizey) Incontinence Severity Score, and FIQOL at the 3, 6, 9 and 12 month time points
- PGI-I scores at the 3, 6, 9 and 12-month time points

The safety endpoint is the safety of the device, as assessed by the number of device-related (Eclipse System) adverse events and device –related serious adverse events, as adjudicated by the Clinical Events Committee (CEC).

Subjects who are screen failures will not be included in the effectiveness endpoint analysis. However, their data will be reviewed to understand reasons for screen failure. All subjects in whom the device was inserted, even if just for fitting, will be included in the safety analysis. For all screen fail subjects, the Investigator or designee will complete Case Report Forms related to the completed visits and a Study Exit Form.

3.6 Primary Effectiveness Analysis

The primary effectiveness analysis is an exact binomial test to evaluate whether the observed response rate is significantly larger than 40% after the first 3 months of the Treatment Period. The analysis will be performed on the ITT population. Subjects who do not complete at least 10 days of diary data at the 3-month time point and who do not continue in the study will be classified as treatment non-responders.

The number and proportion of treatment responders, and its 95% confidence interval, using exact (Clopper-Pearson) confidence limits, will be presented. A p-value for the one-sided upper-tail test of whether the proportion is significantly larger than 0.40, will also be presented.

The null hypothesis will be rejected if a sufficient percentage of subjects exhibit treatment response at the 3 month time point.

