2.3 Recruitment

Potential study subjects will be recruited primarily from practices of participating investigators. All subject recruitment materials will be reviewed and approved by the Sponsor and the governing IRB prior to use.

An estimated 625 subjects will be recruited into this study across all sites. Subjects who qualify via the Baseline diary will proceed with the first fitting visit. Subjects who are successfully fit with the Eclipse System and qualify via the Test Diary will be eligible for treatment. Each site is expected to contribute approximately 7-25% of the total treatment-eligible subjects unless authorized in writing to over-enroll by the Sponsor. Enrollment is competitive until overall enrollment target is reached or study termination by the Sponsor.

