For subjects who previously failed any pelvic exam inclusion/exclusion criteria that allow re-evaluation, their Initial Fitting Visit may be extended up to 6 weeks from the Baseline Visit (without being considered a protocol deviation). The previously failed inclusion/exclusion criteria must be re-evaluated during the Initial Fitting Visit pelvic exam, and must be resolved in order for the subject to continue in the trial. Otherwise, they are exited from the study as a screen failure.

For subjects who were prescribed an estrogen regimen, if the clinician determines that the vaginal tissue has adequately responded to the vaginal estrogen cream and the subject is willing to continue the use of the estrogen cream throughout the remainder of their study participation, they may continue with the Initial Fitting Visit. Otherwise, they are exited from the study as a screen failure.

The following tasks are completed at this visit:

- Inclusion/exclusion criteria reviewed
- Baseline Diary reviewed
- Patient Goal questionnaire – goal identification
- Pelvic exam (speculum and digital rectal exam)
- Trial Insert fitting
- AEs and Concomitant Medications reviewed

Successful fitting with the Trial Insert is defined as an insert that is stable, in the proper position, provides sufficient rectal occlusion based on a digital rectal exam, and is comfortable for the subject. The clinician may try as many different sizes of the Trial Insert as they and the subject agree are tolerable to the subject at the Initial Fitting Visit. If the subject cannot obtain a suitable fit during this Initial Fitting Visit and/or decides to withdraw, the subject is exited from the trial as a screen failure.

Per the eligibility criteria, during the Fitting Visits the subject must demonstrate the ability to properly insert and remove the Trial Insert and inflate and deflate the Insert as needed using the Pump.

If the subject meets the Baseline Diary and Initial Fitting Visit criteria, they are instructed on proper use and care of the Eclipse System (**Appendix 9**), and are scheduled for a Fit Confirmation Visit within 7 days (-5/+7 days) from the Initial Fitting Visit.

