3.11 Power and Sample Size Considerations

Power calculations were performed based on the primary effectiveness analysis, which tests whether the fraction of treatment responders is significantly greater than 0.40 ($H_0: \pi \leq 0.40$ vs. $H_A: \pi > 0.40$) using a one-sided exact binomial test, based on significance $\alpha = 0.025$ and power $1 - \beta = 0.90$.

Based on the LIFE study, we anticipate an 85.6% success rate among study completers and conservatively estimate 21.3% dropout within 3 months, resulting in an estimated 67% response rate in this study. With as few as 40 subjects in the ITT cohort, the study has $\geq 90\%$ power to detect a response rate greater than 40%. Additional subjects, up to the maximum of 150 subjects, will be enrolled through a specified end date in order to provide a more robust analysis.

Withdrawal from the study during the Screening Period is estimated to be quite high due to the baseline diary completion and device fitting requirements. Subjects who are successfully fit with the Eclipse System and successfully complete the Screening Period will be eligible for treatment. Therefore, an estimated 160 to 600 subjects may be recruited into this study in order to achieve 40 to 150 subjects who successfully enter the Treatment Period.

We estimate the subject dropout rate between the start of the Treatment Period and the 12 month visit to be 33%, yielding approximately 25 to 100 subjects completing 12 months of study participation. In a 12 month study of non-surgical management of stress urinary incontinence the dropout rate over this same time period was approximately 36%.²⁹

4 Adverse Events

Investigators and the Sponsor will carefully track and report adverse events. Any subject who is exposed to the Eclipse System, including the Eclipse Insert, the Trial Insert or Sizers (has any Eclipse System device inserted into their vagina) will be included in the Safety Cohort and Safety Endpoint Analysis.

Adverse event definitions are provided in **Table 4**. Based on clinical experience to date the expectation is a very low risk of serious or unanticipated device-related adverse events.

Table 4. Adverse Event Categories

Term	Definition

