8 STATISTICAL ANALYSIS

8.1 General Considerations

Continuous data will be summarized using count (n) the number of non-missing values and mean, median, standard deviation, minimum and maximum as appropriate. The interquartile range (IQR) may also be reported as appropriate. Categorical data will be summarized using counts and frequencies. In general, means and medians will be presented to 1 more decimal place than collected, and standard deviations to 2 more decimal places. Where appropriate, p values will be presented to 4 decimal places.

A one-sided, 2.5% significance level will be used for the primary efficacy endpoint. All p-values, aside from those in the primary efficacy endpoint, are presented for descriptive purposes only. No adjustments will be made for multiple comparisons.

Recorded data may be presented in data listings, aside from cost utilization data which is evaluated under a separate analysis plan. If listed, enrolled subjects will be listed first, followed by screen failures, where appropriate.

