8.5 Pooling Strategy for Study Sites

Data for all sites will be pooled for all safety and efficacy analyses. Study diary success rates per study period may also be summarized by study site in order to evaluate the consistency of effect of treatment by site.

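### The 3-month exact test and interval assume independent women; if response is correlated within site and the result is meant to apply beyond the participating sites, the stated precision is too good, so add a supportive site-clustered interval

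*Protocol*

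**What the plan says.** Protocol 3.6 and SAP 11.1 specify one pooled test of the 3-month response rate in the ITT population: "The primary effectiveness analysis is an exact binomial test to evaluate whether the observed response rate is significantly larger than 40" per cent. The proportion and its 95% interval "using exact (Clopper-Pearson) confidence limits, will be presented". Protocol 3.4 sets the null: "The null hypothesis is that the proportion of treatment responders at 3 months is no more than 40" per cent. SAP 8.1 sets the level: "A one-sided, 2.5% significance level will be used for the primary efficacy endpoint". The same section makes every other p-value descriptive.

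On sites, SAP 8.5 says: "Data for all sites will be pooled for all safety and efficacy analyses". It adds that diary success rates *may* be summarised by site to look at consistency, with no interval and no consequence attached. The synopsis allows up to 15 sites. Protocol 2.3 says: "Each site is expected to contribute approximately 7-25% of the total treatment-eligible subjects", and more with the sponsor's written authorisation.

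At fitting, the site's clinician judges whether the insert is stable, well placed and comfortable, and whether it "provides sufficient rectal occlusion based on a digital rectal exam" (Protocol 2.6.3). Under SAP 8.2 women without a completed diary count as non-responders in the ITT analysis.

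**The concern.** An exact binomial test and a Clopper-Pearson interval are exact only if the responses are independent with a common probability. Several features could make women at one site more alike than women at different sites. The same clinicians size and assess the device, the same staff coach diary completion, and site retention feeds into the endpoint because dropout counts as non-response. With sites supplying up to a quarter of the sample, even weak correlation could noticeably reduce the effective sample size.

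The response rate and its interval are the study's main product. If the interval is read as applying to women fitted at other centres, it may claim more precision than the data carry. The plan names site consistency as a question but does not commit to reporting it.

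**Working it through.** **Inputs.** Null rate 0.40 (Protocol 3.4); one-sided level 0.025 (SAP 8.1); planned rate 0.67 and N from 40 to 150 (Protocol 3.11); up to 15 sites (synopsis); about 7-25% per site (Protocol 2.3). The intraclass correlation ρ is not in the documents. I assume 0.02, 0.05 and 0.10.

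**Step 1: the plan's own figure.** Protocol 3.11 gives 0.856 × (1 − 0.213) = 0.674, hence "resulting in an estimated 67% response rate in this study". At N=40 the smallest count with an upper-tail probability of at most 0.025 under 0.40 is 23. The actual level is 1.89% and power at 0.67 is 92.4%, so the stated 90% or more is reproduced under independence. At N=150 the critical count is 73 and the actual level is 1.93%.

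**Step 2: participating sites only (fixed sites).** If site j has its own rate pⱼ and the enrolment-weighted mean is 0.40, the variance of the total is Σ nⱼpⱼ(1 − pⱼ), which cannot exceed N × 0.40 × 0.60. With four sites of 10 (binomial value 9.6):
- Rates 0.3/0.3/0.5/0.5: variance 9.2, type I error 1.7%, coverage 96.9%.
- Rates 0.2/0.2/0.6/0.6: variance 8.0, type I error 1.1%, coverage 98.0%.

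Variation between these sites makes the planned test and interval conservative.

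**Step 3: sites as a sample of a wider population (random sites).** The variance is multiplied by the design effect DE = 1 + (m̃ − 1)ρ, with m̃ = Σnⱼ²/N. I took beta-binomial responses per site, convolved them exactly, and applied the planned test and interval at N=150.

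- Layout A: 15 sites of 10; m̃ = 10.
- Layout B: 7 sites of 37, 37, 30, 15, 11, 10 and 10 (6.7% to 24.7% each); m̃ = 4184/150 = 27.9.

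| Layout | ρ | DE | Type I error at 40% | Coverage at 67% |
|---|---|---|---|---|
| Either | 0 | 1.00 | 1.9% | 96% |
| A | 0.02 | 1.18 | 2.9% | 94.5% |
| A | 0.05 | 1.45 | 4.3% | 91.7% |
| A | 0.10 | 1.90 | 6.7% | 87.0% |
| B | 0.02 | 1.54 | 4.8% | 90.8% |
| B | 0.05 | 2.34 | 8.9% | 82.6% |
| B | 0.10 | 3.69 | 14.2% | 71.8% |

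Power at 67% is at least 99% in every row. At N=150 the level passes 2.5% once ρ exceeds about 0.012 with 15 equal sites, 0.006 with 8, or 0.003 with 4.

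At N=40 with 8 sites of 5, type I error is 2.3%, 2.9% and 4.0%, and power 91.5%, 90.4% and 88.6%. With 4 sites of 10, power is 88.2% at ρ = 0.05 and 85.0% at 0.10.

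**Step 4: what an adjusted interval looks like.** For 100/150, Clopper-Pearson gives 58.5-74.1%. Korn-Graubard uses the effective size n* = (N/DE) × (t₀.₉₇₅,N−1 / t₀.₉₇₅,J−1)² for J sites. With DE = 1.45, N/DE = 103.4:
- J = 15: (1.976/2.145)² = 0.849, n* = 87.8, interval 55.8-76.4%.
- J = 7: (1.976/2.447)² = 0.652, n* = 67.5, interval 54.1-77.7%.

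Without the t-factor the interval is 56.7-75.6%. In layout B with DE estimated from the data, that shortcut covers only about 92% (ρ = 0.05) and 90% (ρ = 0.10); the full method brings coverage back close to 95%.

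**The case against.** A reader might infer that the 2.5% level and the 95% interval fail whenever response varies by site. The documents do not support that. Step 2 shows the reverse for the participating sites, and neither document defines a wider population of sites as the target. The failure needs both within-site correlation and inference beyond these sites. That wider reading is natural for a device indicated for adult women generally (Protocol 1.9), but it is a reading.

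The size is also assumed. Protocol 1.6.2 reports the earlier six-centre study only in pooled form. At a mean of 40%, ρ = 0.10 puts 95% of true site rates between about 13% and 72%, and ρ = 0.05 between about 20% and 62%; nothing in the documents shows such a spread. Layout B, with three sites at 20-25%, is one permissible pattern at the maximum N, not a forecast. With 15 equal sites and ρ = 0.02 the excess is small.

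The documents do not call fitting operator-dependent. They provide fitter training (Protocol 5.8.2), common instructions (2.6.3.1) and proctoring (2.6.2). Fit failures and Test Diary non-responders leave before the ITT population is formed, so some site differences act before the primary denominator. Differences in later retention and diary completion are not removed.

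Two further strong readings fail. One is that the 6- and 12-month tests lose control of a 2.5% level: SAP 8.1 claims none for them, so only interval width is at issue. The other is that the primary conclusion is in doubt: at the planned 67% it very likely stands.

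What remains is that the plan offers no interval that allows for site and makes its only look at site consistency optional.

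**Conclusion.** The point holds in a limited, conditional form. The primary inference assumes independence. For a claim about sites in general, any appreciable within-site correlation makes the interval too narrow and can push the one-sided level above 2.5%. Under the assumed ρ of 0.02 to 0.10 at N=150, type I error runs from about 3% to 7% with 15 equal sites and from about 5% to 14% with 7 unequal ones; the actual ρ is unknown. For the participating sites alone, the planned analysis is conservative. Error control would matter only if the true rate were near 40%; at 67% the practical effect is on the precision reported. This is a cheap improvement to reporting, not a reason to replace the primary test.

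**What to change.** Keep the exact binomial test and Clopper-Pearson interval as primary.

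- **SAP 8.5:** change the by-site response table from *may* to *will*, and add the pooled rate with the largest site left out.
- **SAP 11.1:** add a site-clustered 95% interval at 3 months, clearly labelled supportive. Use Korn-Graubard with the estimated design effect (not set below 1) and its degrees-of-freedom factor.
- **SAP 11.2.1:** give the same interval at 6 and 12 months, without any claim of error control.

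The cost is a few lines of SAP text and code, and no new data. The downside is a wider second interval, as in step 4. With very few sites it is imprecise and over-conservative: with 4 sites and DE = 4.65 (ρ = 0.10, m̃ = 37.5), n* = (150/4.65) × (1.976/3.182)² = 12.4, and 100/150 would give about 36-90%, which includes 40%. The interval should therefore be supportive only and should not decide the primary result.
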